A two-arm behavioral randomized controlled trial (N=223) will be conducted in partnership with a federally-qualified health center (FQHC) serving a low income, minority population that is at high-risk for significant asthma morbidity. The intervention arm will receive an integrated CHW home intervention for pediatric asthma education. The comparison arm will receive clinic-based certified asthma educator (AE-C) services. Primary Aim 1 is to assess the efficacy of the integrated CHW home asthma intervention, relative to clinic-based AE-C education over 12-months, as demonstrated by asthma control. We hypothesize that the CHW arm will have at least 30% less days with activity limitation than the AE-C arm at 12-months. Specific Aim 2 is to assess maintenance of intervention efficacy, as demonstrated by asthma control at 18 and 24 months after randomization. Specific Aim 3 is to determine the cost-effectiveness at 12-months of CHW and AE-C intervention delivery, and additional costs or savings related to asthma exacerbations at 12- and 24-months. Specific Aim 4 is to assess the efficacy of the integrated CHW home asthma intervention relative to clinic-based AE-C education, as demonstrated by asthma control, among those experiencing depression, stress, and/or a post-traumatic stress disorder. This trial compares the current best practice in asthma self-management education (AE-C services) to an integrated CHW home intervention in which the real-life challenges of patients and the health care system are taken fully into account. This trial will provide clarity as to the expected effect size, cost savings, and resources needed to integrate asthma CHWs into clinical practice.

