3.0 Objectives/Aims

Primary Aim 1: To assess the efficacy of the integrated CHW home asthma intervention, relative to clinic-based AE-C education over 12-months, as demonstrated by asthma control. We hypothesize that the CHW arm will have significantly greater asthma control than the AE-C arm at 12-months as measured by days with activity limitation over the previous 14 days and the Asthma Control Test/childhood Asthma Control Test.

Specific Aim 2: To assess maintenance of intervention efficacy, as demonstrated by asthma control at 18 and 24 months after randomization. We hypothesize that changes in efficacy outcomes will be maintained after cessation of the intervention.

Specific Aim 3: To determine the cost-effectiveness at 12-months of CHW and AE-C intervention delivery, and additional costs or savings related to asthma exacerbations at 12- and 24-months.

Specific Aim 4: To assess the efficacy of the integrated CHW home asthma intervention relative to clinic-based AE-C education, as demonstrated by asthma control, among those experiencing depression, stress, and/or post-traumatic stress disorder (PTSD). We hypothesize that among those living with depression, stress, and/or PTSD, the CHW intervention will be significantly more effective in achieving and maintaining asthma control than the AE-C education intervention.

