9.0 Data Analysis

All analyses will be performed by the investigators and analysts in the Institute for Health Research and Policy using SAS version 9.4. We will compare key population descriptors in the two treatment groups as patient recruitment progresses (at N=100 and N=150) to ensure that the randomization process is achieving reasonable balance, being careful to protect operational staff from bias. Basic summary statistics will be calculated for outcome variables and covariates. Continuous variables will be assessed for normality using Q-Q plots and compared using 2-sample t-tests. If distributions are sufficiently non-normal, then a suitable transformation or non-parametric test will be used. Categorical variables will be compared using chi-square tests. Significance tests will be two-sided at level $\alpha=0.05$.

Specific Aim 1: To assess the efficacy of the integrated CHW home asthma intervention relative to the AE-C intervention at 12-months post-randomization as demonstrated by asthma control. This study will employ two primary measures of asthma control: number of days with activity limitation over the previous 14 days and the Asthma Control Test/childhood Asthma Control Test (ACT/cACT). The mean total number of days with activity limitation over the previous 14-day period will be assessed at 12-months between the two treatment arms using the two-sample t-test or Mann-Whitney test. If the mean days with activity limitation in the intervention arm is at least 30% lower than that of the AE-C arm and $p < 0.05$, we will conclude that the CHW intervention is more effective. The ACT/cACT will be analyzed using similar methods; a MID of 0.2 will be used to determine intervention efficacy. Linear mixed models will

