then be employed to analyze primary outcomes at twelve months. To test the CHW intervention's efficacy on these outcomes, we will first conduct per protocol analyses limited to those patients who received CHW intervention. We will correct potential selection bias by including covariates found to be differentially related to nonadherence. Under the missing at random (MAR) assumption, this ensures unbiased estimates from linear mixed models. Additionally, to test the intervention's effectiveness in clinical practice we will conduct intention-to-treat analyses that include outcomes for all patients randomized. Nonadherent and other subgroups of patients can be expected to exhibit differentially higher rates of missing data. We will therefore examine the sensitivity of inferences to multiple imputation rule using the SAS macros of Little and Yau (1996), including last observation carried forward (LOCF), return to baseline, and continuing on apparent trajectory. The fixed-effects part of the model will be $Days_{ij} = \beta_0 + \beta_1 Time_{ij} + \beta_2 Tx_i + \beta_3 (Tx_i * Time_{ij}) + \epsilon_{ij}$, for subject i at visit j . Candidate covariance structures will be assessed using the data's correlation structure and Akaike's Information Criterion (AIC). A random intercept will be included in the model if it significantly improves the model fit as determined by the likelihood ratio test. Standardized residuals and Cook's distance will be used to assess the influence of outliers and individual observations and residual plots will be used to check the multivariate normal distribution assumption. These analyses will be conducted in SAS PROC MIXED (and PROC GLIMMIX for categorical outcomes), and will be followed by an exploratory variable selection analysis in PROC GLMSELECT. Potentially confounding covariates will be considered for model inclusion using the least absolute shrinkage and selection operator (LASSO) model selection method. This method identifies a significant subgroup of covariates that will form a more parsimonious model. The LASSO method avoids problems typically encountered using stepwise procedures. To accommodate potential age-specific effects, heterogeneity of treatment effects by age will be examined as an exploratory analysis.

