12.0 Statistical Considerations

Statistical analysis is described in Section 9.0. The sample size for the study was determined to allow assessment of the relative efficacy of the proposed interventions with respect to asthma control. While a strong clinical definition of asthma control has been in place for some time, there is no gold standard for assessing asthma control. The Asthma Control Questionnaire (ACQ) has been validated in diverse, large samples but currently there is an absence of substantive data on this test (data such as variability and reasonable effect sizes within this target population) upon which statistical power and sample size estimates can be based. Therefore we have conducted two calculations to ensure adequate power. Using the ACQ, a sample size of 100 per group (total N=200) had power 0.87 to detect the minimally important difference (MID) of 0.5 established for this test.¹⁴ We performed a separate power calculation using number of days with activity limitation (over the past 14-days) as Zeiger et al.⁴² found "activity limitation" to be a strong determinant of the composite asthma control score. In a multi-site inner-city (including Chicago) randomized trial of a home CHW asthma intervention, Morgan et al. reported activity limitations over the previous 14 day period.⁴³ Based on their data, we hypothesize a mean of 3.9 "activity limitation" days at baseline in both groups (SE 0.22) and, in the AE-C comparison group, a mean at 12 months of 2.84 days (SE 0.10). We anticipate the proposed CHW intervention will be more potent than that tested by Morgan et al. because it involves a higher dose and more physician involvement. Within the proposed CHW home intervention group, we anticipate a mean of 2 "activity limitation" days over a 14-day period at 12 months (SE 0.10), representing a 30% reduction from the AE-C comparison group (and 50% reduction from the baseline mean). Further assuming an attrition rate of 15% and 80% power, the standard two-group t-test for comparing means (at 12 months) requires a sample size of about 111 per group, for a total of 223 participants. Analyses to examine heterogeneity of treatment effects by age, race, or other groups have more limited power but results will be considered suggestive for further research.

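### For 12-month activity-limitation days, the 80% power in Section 12 is for the t-test alone; at the planning means, Section 9's two-part efficacy rule is met only about half the time

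*Combined protocol and SAP*

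**What the plan says.** Section 9.0, under Specific Aim 1, names the outcomes: "This study will employ two primary measures of asthma control", namely activity-limitation days over the previous 14 days and the ACT/cACT. For the days outcome, the arms are compared at 12 months by t-test or Mann-Whitney test, two-sided at 0.05. The decision rule follows: "If the mean days with activity limitation in the intervention arm is at least 30% lower than that of the AE-C arm", and p is below 0.05, CHW is concluded to be more effective. Both conditions apply to the observed result. The same section then says that linear mixed models will "then be employed to analyze primary outcomes at twelve months"; no 30% condition is attached to them.

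Section 12.0 assumes an AE-C mean of 2.84 days at 12 months and a CHW mean of 2 "days over a 14-day period at 12 months (SE 0.10), representing a 30% reduction from the AE-C comparison group". It continues: "Further assuming an attrition rate of 15% and 80% power, the standard two-group t-test for comparing means (at 12 months) requires a sample size". The resulting figure is roughly 111 in each arm and 223 overall.

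The hypothesis is worded in two ways. Section 1.0 has the threshold: "We hypothesize that the CHW arm will have at least 30% less days with activity limitation than the AE-C arm at 12-months". Section 3.0 does not: "We hypothesize that the CHW arm will have significantly greater asthma control than the AE-C arm at 12-months".

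**The concern.** The trial is powered for one condition, but the conclusion needs two. A threshold on the observed estimate that equals the assumed true effect is missed about half the time, because the estimate falls on either side of the truth with roughly equal probability. Section 12 gives a single power figure for this outcome, and a reader will naturally take it as the chance of a positive conclusion under Section 9.

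There is also an outcome on which the parts of the plan pull apart: p below 0.05 in favour of CHW with an observed reduction under 30%. The Section 9 rule is not met, but the Section 3 hypothesis would appear to be supported and the mixed model may well be significant. If the plan does not say in advance how these are put together, the emphasis can be chosen after the data are seen.

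**Working it through.** **Inputs from the documents.** Two-sided 0.05, the 30% condition and the tests (Section 9); means 2.84 and 2.00, 80% power, 15% attrition and about 111 per group (Section 12); 1:1 allocation (Section 5).

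**Assumption.** The SD is not stated. Section 12 gives SEs without the n they belong to. The SE of 0.10 cannot be this trial's own per-arm SE: with 95 completers it would imply SD = 0.10 × √95 = 0.97 and t-test power near 100%, not 80%.

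**Planned effect.** (2.84 − 2.00)/2.84 = 0.84/2.84 = 29.6%.

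**The plan's own figure.** 111 × 0.85 = 94.35, taken as 95 completers per arm. With 95 per arm, 80% power needs a standardised difference of 0.4086, so SD = 0.84/0.4086 = 2.06. Run forward by the normal formula, SD 2.05 gives 94 per arm, or 111 after attrition, and SD 2.06 gives 95, or 112. This agrees with 223 in total, but the SD was fitted to that N, so it is not an independent confirmation.

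**The 30% condition.** It is met when (CHW mean − 0.7 × AE-C mean) is zero or less.
- Expected value: 2.00 − 0.7 × 2.84 = 2.00 − 1.988 = 0.012.
- Standard error: 2.06 × √((1 + 0.49)/95) = 0.258.
- Probability: Φ(−0.012/0.258) = Φ(−0.05) = 0.48.

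**Both conditions.** The smallest significant difference is 1.973 × 2.06 × √(2/95) = 0.59 days, which is 20.8% of 2.84. At this SD an observed 30% reduction is therefore practically always significant, and the 30% condition alone sets the joint probability. Simulation with normal means and a pooled t-test gives 0.80 for the t-test, 0.48 for both conditions, and 0.32 for significant but short of 30%. In that last group the observed reduction is roughly 21% to 30%.

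**Range over the unknown SD** (t-test, 95 per arm, means 2.84 and 2.00):

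| SD | t-test significant for CHW | Both conditions | Significant, reduction below 30% |
|---|---|---|---|
| 1.0 | 1.00 | 0.46 | 0.54 |
| 1.5 | 0.97 | 0.47 | 0.50 |
| 2.06 | 0.80 | 0.48 | 0.32 |
| 2.5 | 0.63 | 0.48 | 0.15 |
| 3.0 | 0.48 | 0.45 | 0.03 |
| 3.5 | 0.38 | 0.37 | 0.00 |

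The fall at the highest SDs belongs to the t-test, which becomes the limiting condition. With Mann-Whitney on counts bounded at 0 to 14 (assumed shapes), the joint probability is 0.47 to 0.48 at SD 2.06 and 0.48 to 0.50 at SD 3.5. Strongly skewed counts at a nominal SD of 3.0 gave 0.51 to 0.52 with either test.

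**Rounding.** If 29.5% counts as 30%, the expected value becomes 2.00 − 0.705 × 2.84 = −0.002 and the joint probability is 0.50. It is also 0.50 if the true reduction is exactly 30%.

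**Larger true effects** (SD 2.06, AE-C mean held at 2.84): 0.63 at a 33% reduction, 0.71 at 35%, 0.81 at 38%, 0.86 at 40%.

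**Larger samples** do not help at the planning means: 0.46 with 500 per arm and 0.37 with 5,000, because the true 29.6% lies just below the threshold.

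**The case against.** No stated figure is wrong. Section 12 says in terms that its 80% belongs to the t-test, so what is missing is an operating characteristic, not a correct sum. That stands. A reader might infer that the sample size is miscalculated or that more participants are needed; the documents do not support either. The 80% is attainable for the t-test, and a larger N would not raise the chance of meeting the rule at these means.

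The 30% condition may be a deliberate margin for clinical relevance. It is a legitimate choice, and it does not inflate type I error, since it only adds a hurdle. But Section 9 makes it a condition of the efficacy conclusion, so its probability belongs beside the 80%.

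Section 1 hypothesises a reduction of 30% or more, and with a larger true effect the rule is met more often. That is true, but Section 12 plans on 2.84 against 2.00.

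A reader might infer that the plan reaches no conclusion for a significant result short of 30%. That goes too far: on the ordinary reading of Section 9, superiority is not concluded under that rule. What is open is how this sits with the mixed models and the Section 3 hypothesis.

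Nor is about half the chance that the trial as a whole succeeds. The figure concerns the raw-means rule for one of two primary measures, and does not cover ACT/cACT or the mixed models.

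**Conclusion.** The point holds. The 80% that supports the sample size is not a property of the rule by which Section 9 concludes efficacy on activity-limitation days. At the planning means that rule is met about half the time. This part hardly depends on the SD: 0.46 to 0.48 with the t-test for SDs of 1.0 to 2.5, lower above that with the t-test, and near 0.5 with Mann-Whitney on bounded counts. The specific 48% rests on the assumed SD of 2.06 and on reading 30% without rounding.

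The share of significant results that miss the rule is much less certain: about 32% at SD 2.06, but anywhere from 54% to none over SDs of 1.0 to 3.5. SDs far from 2.06 do not, however, reproduce the sponsor's 80% at this N. The point should be fixed, but it does not call the design into question.

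**What to change.** In Section 12, state the SD used. Next to the 80% for the t-test, give the probability of meeting the Section 9 two-part rule at the planning means: about half, and about 48% if the SD is 2.06. Optionally, add the true reduction at which that probability reaches 80%: about 38% with the AE-C mean held at 2.84 and SD 2.06.

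In Section 9, state that p below 0.05 with an observed reduction under 30% does not meet the rule, and how that result will be reported alongside the mixed-model result.

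The cost is a few sentences in two sections and one short calculation from the sponsor's own SD. Sample size, test and success rule need not change.

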Specific Aim 2: To assess maintenance of intervention efficacy, at 18 and 24 months after randomization. The asthma control measures will be compared between the two treatment groups at 18- and 24-months post-randomization as described above for Specific Aim 1. An indicator variable, to be named "Phase", will be added to the models to allow distinction between the time during intervention periods. The model will be: $Y_{it} = \beta_0 + \beta_1 Time_{ij} + \beta_2 Tx_i + \beta_3 (Tx_i * Time_{ij}) + \gamma_1 Phase_j * (Time_{ij} - 12) + \gamma_2 Tx_i * Phase_j * (Time_{ij} - 12) + \epsilon_{ij}$. We will conclude that any intervention effect is sustained if the slope for $\gamma_2 Time$ after 12-months continues to be positive in the CHW arm.

Specific Aim 3 compares the costs and cost effectiveness of the interventions. The analysis will be conducted from the societal perspective, including the costs borne by the program, individual participant and family, and healthcare system. 1) Cost and resource use information will be collected for the program, participant, and healthcare utilization. 2) Efficacy will be measured as asthma control as described for Specific Aim 1. 3) Cost effectiveness will be evaluated by combining the mean total cost per participant with change in asthma control. We will calculate the ICER for the CHW home intervention compared to AE-C services, such that $ICER_t = (C_1 - C_0) / (E_{1t} - E_{0t})$, where C is cost and E is effectiveness. Subscript 1 denotes CHW home intervention and subscript 0 denotes usual asthma care. t denotes the time period: 12 months, 18 months and 24 months. 95% confidence intervals for the ICERs will be calculated to evaluate the uncertainty in these results. 4) We will conduct one-way and multi-way sensitivity analyses for the key parameters to evaluate whether the ICERs are sensitive to plausible changes in their values. The sensitivity analysis is a check on the robustness and will determine the key parameters impacting the ICERs.

Specific Aim 4: To assess the efficacy of the integrated CHW home asthma intervention among those experiencing depression, stress, and/or PTSD. Interaction terms between treatment indicators for depression, stress, and PTSD will be examined to test for heterogeneity of treatment effects.

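### The ACT/cACT threshold of 0.2 has no unit or source and adds nothing to p<0.05 on its natural reading, and no rule says whether one or both primary measures must succeed

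*Combined protocol and SAP*

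**What the plan says.** Section 9.0, Specific Aim 1, states: "This study will employ two primary measures of asthma control". They are days with activity limitation over 14 days and the ACT/cACT. Testing is at 0.05 ("Significance tests will be two-sided at level" 0.05), with no adjustment for two measures.

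- **Days:** if the CHW mean is at least 30% below the AE-C mean and p<0.05, "we will conclude that the CHW intervention is more effective".
- **ACT/cACT:** "The ACT/cACT will be analyzed using similar methods; a MID of 0.2 will be used to determine intervention efficacy".

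The sections describe success differently:

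- Section 3.0, Primary Aim 1, expects greater control "as measured by days with activity limitation over the previous 14 days and the Asthma Control Test/childhood Asthma Control Test".
- Section 1.0 names days only: "We hypothesize that the CHW arm will have at least 30% less days with activity limitation than the AE-C arm at 12-months".
- Section 9.0 draws the efficacy conclusion from days alone, then gives ACT/cACT its own efficacy statement.

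Section 12.0 has two power calculations, one for days and one for the ACQ. The ACQ is not a primary measure in section 9.0. Its MID of 0.5 is the only sourced MID in the document.

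**The concern.** A minimally important difference should screen out results that are significant but too small to matter. For that it needs a unit, a source and a stated relation to the test. The 0.2 has none of these. If it is too small to bind, one of two primary measures has no clinical threshold in practice. If some other unit was meant, the same ACT/cACT result could pass or fail according to a choice made after unblinding.

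The missing combination rule is a separate gap. With one significant and one non-significant primary measure, section 9.0 supports a positive conclusion and section 3.0 can be read as supporting a negative one. The error rate and the power depend on which applies.

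**Working it through.** **Inputs from the document.** Two-sided 0.05 and the 30% condition (9.0); 12-month means of 2.84 and 2 days, 15% attrition, 80% power, about 111 per group (12.0); cut-off of 20 on ACT/cACT (4.1); 5–7 items (outcome table, 6.8). **Assumed, because not given:** the ACT/cACT SD and effect, the correlation between measures, and a days SD of 3 as a less favourable case.

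**1. The plan's sample size.** Section 12.0 gives standard errors but no SD. With n = 2(1.960+0.842)² SD²/0.84²:
- SD 2.05 gives 93.5, so 94 evaluable; 94/0.85 = 110.6, so 111 per arm.
- SD 2.06 gives 94.4, so 95 evaluable; 95/0.85 = 111.8, so 112 per arm.

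The plan therefore implies an SD of about 2.05–2.06 and 94–95 evaluable per arm.

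**2. Smallest significant difference (t-test), in SD units.** d = t(0.975, 2n−2) × √(2/n). The 0.2-point threshold binds only below SD = 0.2/d. The per-item reading is 0.2×5 = 1.0 to 0.2×7 = 1.4 points.

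| n per arm | d | 0.2 points binds below SD | 1.0 point binds below SD | 1.4 points binds below SD |
|---|---|---|---|---|
| 94 | 1.9728×0.1459 = 0.288 | 0.70 | 3.5 | 4.9 |
| 95 | 1.9727×0.1451 = 0.286 | 0.70 | 3.5 | 4.9 |
| 111 | 1.9708×0.1342 = 0.265 | 0.76 | 3.8 | 5.3 |

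A threshold of 0.2 SD is below d in every row, so it never binds. This is exact for the t-test. For the Mann-Whitney alternative, simulated integer scores gave a significant result with a difference under 0.2 points in at most 0.02% of trials. Under 0.2 SD it was at most 0.06% with normal scores and 0.1–7.4% with left-skewed scores.

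**3. One result, several verdicts.** Assume SD 4, 95 per arm and a difference of 1.2 points: t = 1.2/(4×0.1451) = 2.07, df 188, p = 0.040. It passes in points, in SD units (1.2/4 = 0.30) and per item on 5 items (1.0). It fails per item on 7 items (1.4).

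**4. Either measure suffices.**
- On p alone, two-sided family-wise error is 1 − 0.95² = 9.75% at correlation 0, 9.1% at 0.5 and 7.8% at 0.8.
- With the 30% condition on days, counting only claims that favour CHW (simulation, 95 per arm, null means equal):

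| Null mean, SD of days | corr. 0 | 0.5 | 0.8 |
|---|---|---|---|
| 2.84, 2.06 | 2.5% | 2.5% | 2.5% |
| 2.0, 2.06 | 3.4% | 3.3% | 2.9% |
| 2.84, 3 | 3.6% | 3.5% | 3.0% |
| 2.0, 3 | 4.9% | 4.5% | 3.8% |

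One test alone gives 2.5%.

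**5. Both required, on p alone.** There is no inflation. With 80% power for each (days 2.84 vs 2, SD 2.06; ACT/cACT effect 0.41 SD), joint power is 0.80×0.80 = 64% at correlation 0, 69% at 0.5 and 73% at 0.8. At days SD 3 it is 39–47%.

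**6. ACT/cACT alone.** At 95 per arm the t-test has 80% power for 0.41 SD, 54% for 0.3 SD and 28% for 0.2 SD.

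The simulations use bivariate normal data. That is approximate for a 0–14 count: 17% of a normal with mean 2 and SD 2.06 lies below zero.

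**The case against.** Several stronger inferences are tempting, and the document does not support them.

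- **That the direction is unknown.** Section 3.0 expects greater control with CHW, and section 4.1 treats a score below 20 as uncontrolled, so higher is better. The phrase about similar methods most naturally brings in the t-test or Mann-Whitney test and p<0.05. What remains open is the unit, the source and an explicit link to p.
- **That 0.2 could mean 20%, or apply to change from baseline.** The days rule writes its percentage explicitly, and the ACT/cACT clause has none. Section 9.0 compares arms at 12 months. Points is the natural reading, since section 4.1 uses a score cut-off and the ACQ MID in section 12.0 is a plain score difference.
- **That the trial runs a 9.75% false-positive risk.** That figure ignores the 30% condition and counts results favouring AE-C. It is an upper bound on p alone.
- **That Aims 2 and 3 inherit both gaps.** Aim 2 says "The asthma control measures will be compared between the two treatment groups at 18- and 24-months post-randomization as described above for Specific Aim 1", but it has its own slope rule for a sustained effect. Aim 3 says "Efficacy will be measured as asthma control as described for Specific Aim 1", but it enters change in asthma control into a cost ratio as a quantity, where neither the threshold nor an either/both rule operates.

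It can also be said that days is evidently the deciding measure. Section 9.0 permits that reading, but it does not say what follows if ACT/cACT disagrees, and section 3.0 points the other way. The objections narrow the point without removing it.

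**Conclusion.** The point holds and should be fixed. On the natural reading in points, and also in SD units, 0.2 does not work as a minimally important difference: a significant t-test already exceeds it unless the ACT/cACT SD is below about 0.70–0.76 points. This needs no assumption beyond 94–111 per arm. The per-item reading could bind at plausible SDs, so the unit has to be fixed in advance.

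The conflict over what counts as success also stands on the text alone. Its size depends on assumptions. If either measure suffices, false claims favouring CHW are about 2.5–4.9% against 2.5%, for null means 2.0–2.84, days SD 2.06–3 and correlation 0–0.8; at mean 2.84 and SD 2.06 there is no inflation. If both are required, power on p alone is about 64–73% at days SD 2.06 and an assumed 0.41 SD ACT/cACT effect.

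All figures cover the unadjusted 12-month comparison only, not the mixed models that section 9.0 then describes.

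**What to change.** 1. **Section 9.0, threshold.** Replace 0.2 with a sourced ACT/cACT MID in score points and say that p<0.05 is also required. Or delete the threshold and report the difference with its 95% CI.
2. **Section 9.0, success rule.** State one rule that holds family-wise error at 5%:
   - *Both required:* no alpha adjustment; the cost is the joint power above.
   - *Hochberg across the two:* simulated error 4.3–5.0%. At days SD 2.06, days power on p falls from 80% to 77–78% if ACT/cACT has a 0.41 SD effect, or to 71% if it has none.
   - *Fixed order, days first:* define whether days succeeding includes the 30% condition. At a 0.41 SD effect and days SD 2.06, a p-only gate blocks a significant ACT/cACT result in 7–16% of trials. At SD 3 it blocks 33–42% (0.803 − 0.475 = 0.328 to 0.803 − 0.388 = 0.415). With the 30% condition in the gate, the figures are 33–42% and 35–44%.
3. **Section 12.0.** State that about 95 evaluable per arm detects 0.41 SD on ACT/cACT with 80% power for that test alone. Add the lower probability of an ACT/cACT claim under the chosen rule. At days SD 2.06 this is 64–73% (both required, or fixed order, on p), 39–47% (fixed order with the 30% condition) or 77–78% (Hochberg).
4. **Sections 1.0 and 3.0.** Align the Aim 1 wording with that rule.

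No extra participants, visits or data are needed. If this counts as a major design decision, section 6.2 requires approval by the Community Advisory Board.
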